3.4. Enrollment Strategy

Study subjects will be recruited from the Institution/clinical site's subject database and/or utilizing Independent Ethics Committee (IEC) or Institutional Review Board (IRB) approved materials.

4. STUDY DESIGN AND RATIONALE

4.1. Description of Study Design

This is a 30-Day multi-site, randomized, single-masked, bilateral, controlled, 2-Arm parallel group, dispensing study. Approximately 116 subjects will be screened and randomly assigned to either Test or Control groups (58 subjects/arm). The goal is for a sample size of 104 (52 subjects/arm) after subjects who withdraw or are lost-to-follow-up. Subjects are scheduled for 3 study visits (screening/baseline, 14-Day, and 30-Day follow-up visits) over a period of one month.

At Visit 1, subjects will be consented and screened for inclusion/exclusion criteria. If a subject is found to meet all eligibility criteria, they will be dispensed with artificial tears eye drops based on the randomization scheme; otherwise, the subject will be discontinued from the study. Subjects will be dispensed with their randomly assigned eye drops and instructed to use them in both eyes, 3-4 times a day, or as needed (not exceeding 6 times a day) over a 14 ± 2 day period. The follow-up evaluation (Visit 2) will occur 14 ± 2 days after Visit 1.

JJVC CONFIDENTIAL

At Visit 2, VAS, PRO and MRD questionnaires, SROS and slit lamp findings will be evaluated, and the subject will be dispensed with a new bottle of drops. Subjects will be instructed to use them in both eyes 3-4 times a day until the next scheduled study visit. Visit 3 will take place 30+/-2 days after Visit 1.

At Visit 3, VAS, PRO and MRD questionnaires, SROS, NITBUT and slit lamp findings will be evaluated, and the subject will have a final evaluation before exiting from the study. All used and unused test articles will be collected from the subjects during the exit visit.

4.2. Study Design Rationale

Randomized, masked, controlled designs are the gold standard to perform scientifically sound evaluations of the intervention by reducing bias associated with the conduct and interpretation of a clinical trial and avoiding confounding from other factors. Due to the difference in the shape of the eyedroppers, double masking will not be possible. However, the subjects will be masked from the identity of the lubricating eye drops. A parallel-group design allows for the comparison of the investigational eyedrops to existing marketed product which has received a CE mark in the EU. A 30-Day period is recommended for follow up in pivotal studies and is an appropriate review period based on studies which recognize the impact of cyclical changes to tear quality in female subjects⁸.

5. TEST ARTICLE ALLOCATION AND MASKING

5.1. Test Article Allocation

Subjects will be randomly assigned to a Test group, or a Control group based on a computer-generated randomization schedule prepared before the start of the study in a 1:1 order. Equal number of subjects will be randomized to the 2 treatment arms. The randomization will be stratified by investigational site and randomly permuted blocks will be used within each study site. The randomization scheme will be

generated using the PROC PLAN procedure from the Statistical Analysis System (SAS) Software version 9.4 or higher¹⁰. The study site will follow the randomization scheme provided and will complete enrollment according to the randomization list and will not pre-select or assign subjects. The assignment of the subjects must be performed at the first baseline visit (Visit 1). If there are any Grade 3 or higher other slit-lamp findings, the subject is ineligible to continue at this time, but may return up to one additional time to determine eligibility. The following must have occurred prior to randomization:

- Informed consent has been obtained
- Subject meets all the inclusion / exclusion criteria
- Subject history and baseline information has been collected

When dispensing test articles, the following steps should be followed to maintain randomization codes:

- 1. Investigator or designee (documented on the Delegation Log) will consult the randomization schedule to obtain the test article assignment for that subject prior to dispensing.
- 2. Investigator or designee will record the subject's number on the appropriate line of the schedule.
- 3. Investigator or designee will pull the appropriate test articles from the study supply. All test articles that are opened, whether dispensed (placed on eye or dispensed outside the clinical site) or not, must be recorded on the Test Article Accountability Log in the "Dispensed" section.

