3.3. Exclusion Criteria

Potential subjects who meet any of the following criteria will be excluded from participating in the study:

Exclusion Criteria following Screening

The subject must not:

- 1. Be currently pregnant or lactating.
- 2. Be diabetic.
- 3. Be currently using any ocular medications or have any ocular infection of any type which may interfere with the clinical trial (at the investigator's discretion).
- 4. By self-report, have any ocular or systemic disease, allergies, infection, or use of medication that might contraindicate or interfere with the clinical trial, or otherwise compromise study endpoints, including infectious disease (e.g., hepatitis, tuberculosis), contagious immunosuppressive disease (e.g., Human Immunodeficiency Virus [HIV]), autoimmune disease (e.g., rheumatoid arthritis, Sjögren's syndrome), or history of serious mental illness or seizures. See section 9.1 for additional details regarding excluded systemic medications.
- 5. Have habitually worn rigid gas permeable (RGP) lenses, orthokeratology lenses, or hybrid lenses (e.g., SynergEyes, SoftPerm) within the past 3 months or soft contact lenses in the past 1 month.

- 6. Have participated in any pharmaceutical or medical device related clinical trial within 30 days prior to study enrollment.
- 7. Be an employee (e.g., Investigator, Coordinator, Technician) or immediate family member of an employee (including partner, child, parent, grandparent, grandchild or sibling of the employee or their spouse) of the clinical site.
- 8. Be a current habitual user of prescription medication to treat dry eye and ocular discomfort, ocular steroids, or any medication (RX or OTC), except for artificial tears that would interfere with the clinical study (at the discretion of the investigator).
- 9. Have any known allergy or sensitivity to ingredients that the investigational product may contain (e.g., Sodium Chlorite, Boric Acid, Sodium Borate Decahydrate, Sodium Chloride, Potassium Chloride, Calcium Chloride Dihydrate, Magnesium Chloride Hexahydrate, Polyethylene Glycol 400, Sodium Hyaluronate and Purified Water).

Exclusion Criteria at Baseline Evaluation

The subject must not:

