5.2. Masking

Masking will be used to reduce potential bias. Due to the difference in shape of the marketed eye drops compared to the test eye drops, double masking is not possible. However, the subjects will be masked from the identity of the eye drops. The identity of the investigational products will be masked by over labeling the eye drop bottles with a label containing the study number, expiration date and the randomization codes. Investigators and clinical site personnel involved in the data collection will not be masked as to the identity of the investigational product.

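### Unmasked site staff read each assignment from a randomization schedule supplied to the site, and no step conceals the later lines, so selection bias is possible

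*Combined protocol and SAP*

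**What the plan says.** Section 5.1 has the schedule generated by computer before the study starts, 1:1 and stratified by site, and "randomly permuted blocks will be used within each study site". It then gives the site procedure: "The study site will follow the randomization scheme provided and will complete enrollment according to the randomization list". The investigator or designee "will consult the randomization schedule to obtain the test article assignment for that subject prior to dispensing", records the subject's "number on the appropriate line of the schedule", and takes the matching product from stock.

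On masking, section 5.2 describes "over labeling the eye drop bottles with a label containing the study number, expiration date and the randomization codes". This is meant to mask subjects. For staff it is explicit: "Investigators and clinical site personnel involved in the data collection will not be masked as to the identity of the investigational product". It also says that the two bottles differ in shape.

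Eligibility leaves room for judgement. Exclusions 3, 8 and 13 in section 3.3 are discretionary; exclusion 8, for example, reads in part "except for artificial tears that would interfere with the clinical study (at the discretion of the investigator". A Grade 3 or higher slit-lamp finding makes the subject ineligible for the moment, but the subject "may return up to one additional time to determine eligibility".

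Section 5.1 also tells sites not to pre-select or assign subjects, and requires consent, eligibility and baseline data before randomization. Section 10 prohibits waivers.

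**The concern.** Randomization prevents selection bias only if the person deciding on entry does not know the next assignment. Section 5.1 reads as a multi-line list held at the site and used by people who may also recruit and assess subjects. Foreknowledge could change whom they approach, in what order, how they apply the discretionary exclusions, or whether they grade a borderline slit-lamp finding as Grade 3 and defer the subject to a return visit.

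The masked subject rates the primary endpoint, which limits bias in the rating. It does nothing about selection before randomization. Nor can the analysis be relied on to repair it. The Plan A equation in section 14.5 includes baseline VAS and would absorb an imbalance in that variable. Plan B, used if the Shapiro-Wilk test rejects normality, describes no covariate adjustment. Section 14.2 itself warns that the data may be non-normal, so Plan B is a real prospect. Neither plan corrects selection on unmeasured prognosis.

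**Working it through.** **1. Is concealment described anywhere?**

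- Section 5.1 has the site consult a list, write on its line and pull product. It gives no release mechanism.
- Sections 5.2 and 6.4 describe over-labelling, which masks subjects only.
- Section 5.3 covers breaking the mask, not the period before assignment.
- Section 6.7 requires a locked cabinet open only to those assigned to dispense. This controls stock, not the list.
- Section 7.2 places baseline VAS at step 1.8, eligibility at 1.13 and randomization at 1.15. Step 1.15 says only that subjects are randomized.
- Section 13.4.1 mentions breaking the randomization code, again only after assignment.
- Section 15.1 describes the electronic system for data capture only.

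No section mentions sealed envelopes, central or interactive assignment, line-by-line release, or an independent holder of the list.

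**2. Would a coded list conceal the arm?** Not reliably. The codes are on the bottle labels, the bottles differ in shape and staff are unmasked, so anyone who sees the stock can link a code to a product.

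**3. Site size.** Table 10 (SD 30, 10% dropout) reproduces. The t-test needs 49 per arm, as in Table 9. Then 49 × π/3 = 51.3, rounded up to 52; 52/0.90 = 57.8, rounded up to 58; and 2 × 58 = 116. Over 8 sites that is 116/8 = 14.5 subjects, consistent with 12-16 in Table 1.

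**4. Predictability if later lines are readable.** All 12-16 assignments at the site.

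**5. Predictability if later lines are hidden.** Unmasked staff can still track past assignments. Block size is not stated, so fixed, known sizes of 2, 4 and 6 are assumed. With *a* Test and *c* Control assignments left in a block, the best guess is right with probability max(*a*, *c*)/(*a* + *c*). The assignment is certain when *a* or *c* is 0. Averaging over all orderings gives, position by position:

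- Size 2, correct: 1/2, 1. Mean 1.5/2 = 75.0%.
- Size 4, correct: 1/2, 2/3, 2/3, 1. Mean 2.833/4 = 70.8%.
- Size 6, correct: 0.5, 0.6, 0.6, 0.7, 0.7, 1. Mean 4.1/6 = 68.3%.

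The expected share of certain assignments in a block of 2*m* is 1/(*m* + 1).

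| Assumed block size | Guess correct | Certain | Per 12 subjects: correct / certain | Per 16 subjects: correct / certain |
|---|---|---|---|---|
| 2 | 75.0% | 50.0% | 9.0 / 6 | 12.0 / 8.0 |
| 4 | 70.8% | 33.3% | 8.5 / 4 | 11.3 / 5.3 |
| 6 | 68.3% | 25.0% | 8.2 / 3 | 10.6 / 3.1 |

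For size 6 and 16 subjects, the last block is cut after four positions: 8.2 + (0.5 + 0.6 + 0.6 + 0.7) = 10.6 correct, and 3 + 0.1 = 3.1 certain.

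The table gives the foreknowledge that remains once later lines are hidden. It does not measure bias in the VAS score, which cannot be derived from the documents.

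**The case against.** The strongest reply is that this argues from silence. Section 5.1 says what staff do, not what the list looks like, and a site instruction outside these documents may conceal the later lines. That stands as a limit: visibility is inferred, and bias is possible rather than shown. But the procedure as written can be followed in full without concealing anything.

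Second, the list may show only codes. The sample label in section 6.4 carries a one-letter code, and sections 5.3 and 13.4.1 read as if assignment were not openly known at the site. Those sections conflict with the plain statement in 5.2 and should be reconciled with it. They concern unmasking after assignment and hide nothing beforehand. One label does not settle how codes map to arms, but unmasked staff handling visibly different bottles can learn it.

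Third, safeguards exist. The ban on pre-selection is an instruction rather than a mechanism. The order of steps protects the baseline rating but does not hide the next line. The locked cabinet and the use of a designee would allow dispensing to be separated from recruitment, but nothing requires it.

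Fourth, Plan B analyses change from baseline, so baseline VAS enters by subtraction. That is correct, but it is not full adjustment and does not remove regression to the mean.

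**Conclusion.** The concern holds. As written, section 5.1 leaves allocation unconcealed from unmasked staff who also make discretionary entry decisions. With a readable list, up to 100% of a site's assignments are foreseeable. With later lines hidden, 25-50% remain certain and 68-75% guessable under assumed fixed, known blocks of 2 to 6. The conclusion rests on the text of section 5.1 and on the absence of any release mechanism elsewhere in the documents. It does not show that selection would occur, and it implies no particular VAS shift. In a confirmatory trial meant to support registration, this should be corrected. Sample size, alpha and power are unaffected.

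**What to change.** Replace steps 1 and 2 of section 5.1 with text such as:

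> After eligibility is recorded at step 1.13, the delegate opens the next sequentially numbered, opaque, sealed envelope for the site, writes the subject number on it, and signs and dates it at opening. The full schedule and the block sizes, which vary, are not given to sites.

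Where staffing allows, someone who does not enrol subjects should hold the envelopes, and the monitor should check opened envelopes against enrolment dates. Release through the electronic data capture system is an alternative only if that system supports it. If concealed release is already in use, one sentence in 5.1 saying how it works and who holds the list is enough.

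The cost is one paragraph and 116 envelopes, or 8 × 16 = 128 at the upper site figure in Table 1, plus spares for replacement subjects. No visits or subjects are added. The downsides are minor logistics and, with varying blocks at 12-16 per site, a possible incomplete last block and slight imbalance, although 5.1 also promises equal numbers per arm. Some predictability will remain, because staff are unmasked and blocks are within site.

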5.2. Masking

Masking will be used to reduce potential bias. Due to the difference in shape of the marketed eye drops compared to the test eye drops, double masking is not possible. However, the subjects will be masked from the identity of the eye drops. The identity of the investigational products will be masked by over labeling the eye drop bottles with a label containing the study number, expiration date and the randomization codes. Investigators and clinical site personnel involved in the data collection will not be masked as to the identity of the investigational product.

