1.4. Summary of Known Risks and Benefits to Human Subjects

The following risks/adverse events can be associated with using artificial tears, in general:

- There may be less comfort than when the drop was first placed on the eye.
- The eyes may burn, sting and/or itch.
- There may be a feeling of something in the eye (foreign body, scratched area).
- There may be the potential for some temporary impairment due to peripheral infiltrates, peripheral corneal ulcers, and corneal erosion.
- There may be the potential for other physiological observations, such as local or generalized edema, corneal neovascularization, corneal staining, injection, tarsal abnormalities, iritis, and conjunctivitis, some of which are clinically acceptable in low amounts.
- There may be excessive watering, unusual eye secretions, or redness of the eye.
- Poor visual acuity, blurred vision, rainbows or halos around objects, photosensitivity, or dry eyes may also occur if the drops are used continuously or for too long a time.

There is no direct benefit to the subject for participating in the study, although they will be able to try out new artificial tears. The information from this study will aid in the further development and design of new artificial tears.

For the most comprehensive clinical information regarding the control eyedrops refer to the package insert (Appendix C).

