3.2. Inclusion Criteria

Potential subjects must satisfy all of the following criteria to be enrolled in the study:

Inclusion Criteria following Screening

The subject must:

- 1. Read, understand, and sign the STATEMENT OF INFORMED CONSENT and receive a fully executed copy of the form.
- 2. Appear able and willing to adhere to the instructions set forth in this clinical protocol.
- 3. Be between 18 and 69 (inclusive) years of age at the time of screening.
- 4. Possess a wearable pair of spectacles that provide correction for distance vision and bring them to every visit (only if applicable- to the investigator's discretion).
- 5. Self-reported symptoms of ocular dryness and/or the use of artificial tears in the last 3 months.
- 6. Subjects must be non-contact lens wearers.

Inclusion Criteria at Baseline Evaluation

7. The monocular, distance visual acuity must be 20/30 or better in each eye, either unaided or best corrected.

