7.2. Detailed Study Procedures

VISIT 1

Aim for Visit 1 to occur in the afternoon (After 12 PM). The subjects must present to Visit 1 wearing their spectacles (if applicable). Subjects will be requested to bring their habitual artificial tears with them to the visit (if applicable).

	Visit 1: Screening			
Step	Procedure	Details		
1.1	Statement of Informed Consent	Each subject must read, understand, and sign the Statement of Informed Consent before being enrolled into the study. The Principal Investigator or his/her designee conducting the informed consent discussion must also sign the consent form. NOTE : The subject must be provided a signed copy of this document.		
1.2	Demographics	Record the subject's year of birth, age, gender, race, and ethnicity.		
1.3	Medical History and Concomitant Medications	Questions regarding the subject's medical history and concomitant medications.		
1.4	Artificial Tear Use	The subject will be asked about their artificial tear use		
1.5	Eligibility after Screening	All responses to Screening Inclusion Criteria questions must be answered "yes" and all responses to Exclusion Criteria must be answered "no" for the subject to be considered eligible. If subject is deemed to be ineligible after screening, proceed to Final Evaluation and complete Subject Disposition. Refraction and Biomicroscopy forms are not required.		

	Visit 1: Baseline			
Step	Procedure	Details		
1.6	Entrance Visual Acuity	Record the distance high contrast visual acuity to the nearest letter (OD, OS, and OU) with their habitual spectacle correction in place (or unaided if applicable).		
1.7	Baseline Subject Reported Ocular Symptoms	Subjects will respond to a verbal open- ended symptoms questionnaire.		
1.8	Baseline VAS	The subject will respond to the VAS questionnaire using the Kiosk portal.		
1.9	Baseline PRO questionnaires	The subject will complete the electronic questionnaires using the Kiosk portal.		
1.10	Tear Break up Time	Record the tear film stability (NIBUT), OD and OS, with a Medmont or other topographer.	NIBUT work aid (Appendix D)	
1.11	Slit Lamp Biomicroscopy	The FDA slit lamp classification scale will be used to grade the findings and determine eligibility.		

	Visit 1: Baseline			
Step	tep Procedure Details			

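### Subject masking rests on an over-label although the bottle shapes differ, and habitual users of the marketed Control are eligible, so masking may not hold for them

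*Combined protocol and SAP*

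**What the plan says.** Section 4.2 explains the single-masked design: "Due to the difference in the shape of the eyedroppers, double masking will not be possible". Section 5.2 gives the same reason ("Due to the difference in shape of the marketed eye drops compared to the test eye drops, double masking is not possible") and then, with no qualification, "However, the subjects will be masked from the identity of the eye drops". The means is a label: "The identity of the investigational products will be masked by over labeling the eye drop bottles with a label containing the study number", together with the expiration date and randomization code. Sections 6.1 and 6.4 describe the same over-label and nothing further. Section 5.2 adds that investigators and site staff involved in data collection are not masked.

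On eligibility, inclusion 5 in Section 3.2 reads "Self-reported symptoms of ocular dryness and/or the use of artificial tears in the last 3 months", with no restriction by brand. Exclusion 8 in Section 3.3 covers prescription dry-eye treatment, ocular steroids "or any medication (RX or OTC), except for artificial tears that would interfere with the clinical study". Section 1.2 describes the Control as a marketed product sold without a prescription. Section 7.2 asks subjects to bring their habitual drops to Visit 1, and step 1.4 asks about artificial-tear use.

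Under Section 2.2, subjects rate overall comfort (primary) and quality of vision (secondary) on 0 to 100 VAS scales.

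**The concern.** With site staff unmasked, masking of the subject is the only masking in the trial, and it protects two endpoints that the subject scores. The label conceals the printed identity. It does not conceal the feature that, by the protocol's own account, distinguishes the two products.

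A subject who does not know Blink Tears sees one over-labelled bottle in this parallel-group design and has nothing to compare it with. A habitual Blink Tears user is in a different position. Assigned to Control, that subject may recognise the usual bottle. Assigned to Test, the unfamiliar shape may show that this is the other product. Nothing in Sections 3.2 or 3.3 keeps such subjects out.

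If knowledge of the arm changes how these subjects score, Test minus Control is biased. A bias towards Test makes the non-inferiority conclusion too easy to reach. A bias against Test costs power. The analyses in Sections 14.5 to 14.7 could not tell either case from a true effect.

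**Working it through.** **Does the text close the gap?**

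| Link | Where | Finding |
|---|---|---|
| Products differ visibly | 4.2, 5.2 | Stated; given as the reason double masking fails |
| Shape concealed from subjects | 5.2, 6.1, 6.4 | No; over-label only |
| Blink Tears users kept out | 3.2, 3.3 | No; inclusion 5 has no brand limit, exclusion 8 exempts artificial tears |
| Subject handles the bottle | 7.2, step 1.16, then home use | Yes |
| Subject rates the endpoints | 2.2 | Yes, both VAS scores |
| Stratification by prior use | 5.1 | No; by site only |
| Analysis by prior use | 14.5 to 14.7 | None; the planned sensitivity analysis is on the per-protocol set, which removes major deviations, and Table 7 lists nothing about prior brand |

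Section 5.3 deals only with deliberate breaking of the mask.

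**The plan's own sample size.** Inputs from Section 14.2: SD 30, margin -20, true difference 0, power 90%, one-sided 0.025 (the two-sided 0.05 of the text), 10% dropout.

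- Two-sample t-test, noncentral t: 49 per arm, as in Table 9.
- Wilcoxon: 49 × π/3 = 51.3, so 52 per arm, as in Table 10.
- Dropout: 52 / 0.90 = 57.8, so 58 per arm and 116 in total, as stated.

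The plan's figures reproduce, and none is disputed here.

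**What a shift would do (illustration).** The documents give neither the share f of subjects who recognise their arm nor the change b in those subjects' between-arm VAS difference. Both are assumptions. The overall shift is s = f × b.

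- SE = 30 × √(2/52) = 5.88; df = 102; one-sided 2.5% t critical value 1.983.
- Error at the margin when the shift favours Test: P(T > 1.983), T noncentral t with noncentrality s / 5.88.
- Power at true difference 0 when the shift is against Test: P(T > 1.983), noncentrality (20 − s) / 5.88.

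| Shift s (VAS points) | Example f × b | One-sided error if towards Test | Power if against Test |
|---|---|---|---|
| 0 | none | 2.5% | 92.0% |
| 0.5 | 10% × 5 | 3.0% | 90.7% |
| 1 | 10% × 10 | 3.7% | 89.2% |
| 2 | 20% × 10 | 5.2% | 85.8% |
| 4 | 20% × 20 | 9.9% | 76.8% |

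Power with no shift is 92.0% rather than 90% because this is the t-test evaluated at the 52 per arm that the plan derived for the Wilcoxon test.

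**The case against.** The protocol is open about being single-masked and says why. Recognition is an inference: the documents do not describe how distinctive the over-labelled control bottle is, and the group concerned may be very small. This stands, and it is why the point is that masking may not hold for these subjects, not that it fails.

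The assumed effects may also be too large. Table 8 gives a mean 30-day change on Blink Tears of 12.5 points, so a 10 to 20 point expectation effect equals 80% to 160% of that change (10/12.5 and 20/12.5). With 5 points and a 10% to 20% share, the shift is 0.5 to 1 point against a 20-point margin. This also stands; the upper rows of the table are not forecasts.

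A reader might infer that recognition must favour Test, because Section 1.4 says of subjects "although they will be able to try out new artificial tears". The documents do not support that. The phrase is protocol text on risks and benefits, in a sentence that also says there is no direct benefit to the subject, and it does not show what subjects are told. Someone who chose Blink Tears could equally favour the familiar drop, which would work against Test.

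Finally, exclusions 3 and 8 leave room for investigator discretion, and step 1.4 may already capture brand; the case report form is not shown. Discretion is not a rule, however, and exclusion 8 expressly exempts artificial tears. Even if brand is recorded, no analysis using it is planned.

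**Conclusion.** The concern holds in a limited form. The unqualified masking statement in Section 5.2 is not secured for habitual Blink Tears users, who are eligible, may recognise the bottle, and score both confirmatory endpoints. Subjects unfamiliar with Blink Tears are not unmasked by shape alone, so a general failure of masking does not follow.

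The actual size and direction of any bias cannot be determined from the documents. The illustrative figures rest on SD 30, 52 per arm, the t-test and an assumed overall shift. They show that a shift small relative to the margin could still matter: 2 points towards Test roughly doubles the one-sided error, and 2 points against Test costs about 6 percentage points of power (92.0% to 85.8%). This is a weakness worth correcting cheaply in a confirmatory trial, not a flaw that invalidates the design.

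**What to change.** Preferred: add to Section 3.3 an exclusion of subjects who have used Blink Tears in the control bottle within the 3-month window already used in inclusion 5. Check it at step 1.4 against the drops brought to Visit 1. The cost is one line, slightly slower recruitment and a slightly narrower population.

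Alternative, if the sponsor prefers to keep these subjects: make sure the habitual brand is recorded at step 1.4, pre-specify in Sections 14.5 and 14.6 a sensitivity analysis of both endpoints without habitual Blink Tears users, and qualify the statement in Section 5.2 to say that subjects familiar with the marketed bottle may recognise it. The cost is one data item, if it is not already collected, and one extra analysis with somewhat fewer subjects.

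Neither option changes the visit schedule or the treatment. A question at Visit 3 asking subjects to guess their arm is not recommended: after 30 days of use the answer is confounded with perceived comfort and would not cleanly measure unmasking.
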